**Appendix VIII**

**Modified Barium Swallow Study Form**

**MBS**

**Modified Barium Swallow Study Form**

**E3311: Phase II Randomized Trial of Transoral Surgical Resection followed by Low-dose or Standard-dose IMRT in Resectable p16+ Locally Advanced Oropharynx Cancer**

**INSTRUCTIONS:** To be filled out by the speech pathologist after the modified barium swallow study. **Dates are recorded as mm-dd-yyyy unless otherwise specified.**

**MBS PROTOCOL:**

All MBS studies must follow a standard protocol as outlined below.

Additional bolus presentations or swallowing strategies may be tested after completing bolus trials in the study protocol, at the discretion of the clinician conducting the MBS study.

Studies will be done in lateral and AP views with focus fixed on the soft palate superiorly, cricopharyngeus inferiorly, lips anteriorly, and cervical spine posteriorly.

Video-recordings will require time code imprints accurate to 0.01 seconds (30 frames/second). Video-recordings between 15-30 frames/second will be accepted as long as the recording rate is clearly documented in advance. Video-recordings below 15 frames/second will not be accepted.

Studies must be recorded in AVI or MPEG format. All centers must use the Kay Digital Swallowing Workstation for the studies; or alternatively, have the ability to convert files to AVI or MPEG format.

Centers must use Varibar products. Consistencies and quantities are listed below. Liquids must be administered first to avoid confounding the results from remaining residue in the pharynx after solid consistencies.

A dime must be taped to the subject's chin during the swallowing study. The circular shape of the dime minimizes the impact of head rotation and the known diameter of the dime allows for calibration of pixels per cm and thus calculation of distances and areas on the lateral view of the x-ray.

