**Appendix VI**

**Modified Barium Swallow (MBS) Credentialing Checklist**

**This form needs to be completed by the institution before patients can be registered to E3311. Once the form is complete, please fax this to the ECOG-ACRIN Operations Office - Boston at [contact], Attention: E3311 Data Manager. You will receive an email from the ECOG-ACRIN Data Manager confirming the receipt of the checklist.**

Rev. 7/13

1. Do you conduct modified barium swallow (MBS) studies to evaluate swallowing disorders in your institution?  
YES \_\_\_\_\_ NO \_\_\_\_\_  
If "NO", skip to number 8; if "YES", please answer questions 2-8.
2. Are your MBS videos recorded digitally at a minimum frame rate of 30 frames/second (i.e., accurate to 0.01 time code imprints)?  
YES \_\_\_\_\_ NO \_\_\_\_\_
3. Do you use the Kay Pentax Digital Swallowing Workstation (this is NOT mandatory for participation)?  
YES \_\_\_\_\_ NO \_\_\_\_\_
4. Do you use Varibar contrast agents specified in this protocol, including Varibar Thin Liquid and Varibar Pudding?  
YES \_\_\_\_\_ NO \_\_\_\_\_
  - a. If no, can you access Varibar contrast agents for MBS studies conducted per E3311  
YES \_\_\_\_\_ NO \_\_\_\_\_
5. Are you (speech pathologists) willing to follow the MBS protocol as written in E3311 (including the sequence of bolus administration, use of Varibar products, and volumes/viscosities specified)?  
YES \_\_\_\_\_ NO \_\_\_\_\_
6. Please provide the following data specific to your site:
  - a. Number of speech pathologists at your institution who perform MBS studies?  
\_\_\_\_\_
  - b. Average number of total MBS studies conducted at your institution each week?  
\_\_\_\_\_
  - c. Average number of MBS studies conducted on patients who have head and neck cancer each week? \_\_\_\_\_

---

7.

---

**Signature of Speech Pathologist  
completing this form**

---

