**Lateral view:**

- 5mL thin (2 trials, tsp). Instruction to the patient: *please hold this in your mouth until asked to swallow.*
- 20mL thin (1 trial). Instruction to the patient: *please try to take the whole amount and hold it in your mouth until I ask you to swallow.* Self administration is optimal, but clinician administration is acceptable.
- 5mL pudding (1 trial tsp). Instruction: *swallow when you are ready.*
- 1/2 cookie or cracker, barium coated - coated with 3 ml (1/2 tsp) of Varibar pudding (1 trial). Instruction to the patient: *chew this up and swallow when you feel comfortable and ready to swallow.*

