**A-P view:**

10mL thin (1 trial). Instruction: slightly raise your chin (neutral position, not tucked or extended), hold this in your mouth until asked to

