**RATING RULES:**

Rate MBS outcomes below on the basis of bolus trials in the ECOG-ACRIN protocol. Do not rate based on additional bolus trials that are administered outside of the protocol or based on bolus trials in which a swallow strategy/posture was tested. Please select a SUMMARY RATING based on the highest level of impairment you observe on any bolus trial in the protocol.

MBS
 Modified Barium Swallow Study Form			
E3311: Phase II Randomized Trial of Transoral Surgical Resection followed by Low-dose or Standard-dose IMRT in Resectable p16+ Locally Advanced Oropharynx Cancer			
1 DATE OF MBS ____ - ____ - ____	2  TIME OF MBS 1. Baseline 2. After surgery (before adjuvant therapy) 3. Six months after treatment 4. Twenty-four months after treatment		
Outcome Variables	Definition	Scoring Rules (Rate the worst of impairment across all bolus trials in the MBS protocol)	Rating
3 LARYNGEAL PENETRATION	PENETRATION: Bolus enters the larynx but does not pass below the TVFs	Select "1" if LARYNGEAL PENETRATION occurred on any bolus in the protocol.	 No penetration (0)  Penetration (1)
4 ASPIRATION	ASPIRATION: Bolus enters the larynx and passes below the TVFs. SENSATE: attempts to eject aspirate from airway (e.g., cough, throat clear) SILENT: no effort to eject aspirate from airway (no cough, throat clear)	Select the highest level of aspiration that occurred during the protocol. Select "1" if SENSATE ASPIRATION occurred on any bolus in the protocol, but silent aspiration NEVER occurred. Select "2" if SILENT ASPIRATION occurred on any bolus in the protocol.	 No aspiration (0)  Yes, sensate (1)  Yes, silent (2)

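### Appendix VIII requires liquids before solids in the swallow study, yet lists a thin-liquid A-P bolus after pudding and cookie and counts it towards the penetration and aspiration ratings

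*Combined protocol and SAP*

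**What the plan says.** Appendix VIII (MBS Protocol) makes the procedure compulsory: "All MBS studies must follow a standard protocol as outlined below". It sets an order and gives the reason: "Liquids must be administered first to avoid confounding the results from remaining residue in the pharynx after solid consistencies". On views it says: "Studies will be done in lateral and AP views".

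The list is grouped by view. The lateral view opens with "5mL thin (2 trials, tsp"), goes on to one 20 mL thin trial, then "5mL pudding (1 trial tsp"), and ends with a pudding-coated half cookie or cracker. The A-P view, printed next, has a single entry: "10mL thin (1 trial). Instruction: slightly raise your chin".

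The rating rules say: "Please select a SUMMARY RATING based on the highest level of impairment you observe on any bolus trial in the protocol". They leave out only boluses given outside the protocol and those used to test a swallowing strategy or posture.

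Appendix VI, item 5, asks the site's speech pathologists whether they will follow the MBS protocol as written, "including the sequence of bolus administration, use of Varibar products, and volumes/viscosities specified".

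Section 10.1.6 calls swallowing a secondary endpoint. It has the prevalence of penetration, aspiration and residue estimated at each time point and compared between arms.

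**The concern.** The protocol names its own confounder: residue that solids leave in the pharynx. A thin bolus swallowed after pudding and cookie meets exactly that condition. A worst-finding rule does not average such a bolus away, because a single finding on it sets the score. Penetration or aspiration seen only on that bolus may reflect leftover solid carried into the airway rather than how the patient handles thin liquid.

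Appendix VI also asks sites to commit to a sequence, while Appendix VIII supports two. A site that follows the list and a site that follows the liquids-first sentence would record the same item under different conditions. What is at stake is the absolute prevalence of penetration and aspiration and their comparability between sites. Section 1.8 presents MBS as the trial's main objective measure of function, so these ratings will be read closely even though the endpoint is secondary.

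**Working it through.** No design figure is involved and the plan states none on this point. The check is a count of the listed boluses followed by a reading of each rating item.

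**Listed boluses (Appendix VIII, lateral view then A-P view)**

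| Order as printed | View | Bolus | Trials |
|---|---|---|---|
| 1–2 | Lateral | 5 mL thin | 2 |
| 3 | Lateral | 20 mL thin | 1 |
| 4 | Lateral | 5 mL pudding | 1 |
| 5 | Lateral | Coated half cookie or cracker | 1 |
| 6 | A-P | 10 mL thin | 1 |

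Total: 2 + 1 + 1 + 1 + 1 = 6. Thin liquid: 2 + 1 + 1 = 4. Pudding or cookie: 1 + 1 = 2. Three of the four thin boluses come before the pudding and cookie; the fourth is printed after both.

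**Does the sixth bolus count?** Yes. It is in the protocol, so the first exclusion does not apply. It is not a posture trial either: the instruction describes the head position as neutral. All six boluses feed the summary rating.

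**Which items can it change?**

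- *Item 3, penetration (no/yes).* The score is positive if any of the six is positive. The A-P bolus changes it only in a patient with no penetration on the other five, one of which is a 20 mL thin bolus, twice the A-P volume.
- *Item 4, aspiration (none, sensate, silent).* The score is the worst grade of the six. The A-P bolus changes it only when its grade is worse than on all of the other five.
- *Item 5, residue.* This is judged after the first swallow, as a share of the bolus just given. The pudding and cookie are already scored in their own right, and cookie left behind is not residue of the thin bolus. The A-P bolus would have to leave a larger share of itself than any other bolus did. Carry-over gives no evident route to that, so item 5 is unlikely to be affected.

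**The two ways a site can proceed**

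- *Follow the print order.* Bolus 6 breaks the liquids-first rule, and items 3 and 4 can rest on it.
- *Follow the liquids-first sentence.* The A-P thin bolus moves ahead of the pudding. The rule is kept, but the procedure differs from that of a site following the list.

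The size of the effect would need three rates: residue after the solids, conversion to penetration or aspiration on the next thin bolus, and the share of patients not already positive. The documents give none of them, so no prevalence shift is computed.

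**The case against.** The strongest reply is that the conflicting order is inferred. No sentence says the A-P view follows the lateral view. The boluses are not numbered across views, and the appendix introduces them as a list of consistencies and amounts. The only explicit instruction on order is the liquids-first sentence, and the list can be read to comply with it. This stands in part: the fault may be an ambiguity rather than an outright contradiction. It does not remove the problem, because the list is the only full sequence on paper and Appendix VI asks sites to keep to a sequence. Nor can liquids-first mean merely that the study starts with liquids, since the stated reason covers any liquid given after solids.

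A reader might infer three stronger things, which the documents do not support:

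- *That all three ratings are contaminated.* Item 5 is scored per bolus and already counts the solids.
- *That the comparison of arms is biased.* The same appendix applies to every arm and visit, and Arms B and C are randomized. Carry-over could differ if retained residue differs by arm or visit, but nothing in the documents shows that it does. Part of any such difference would also be real impairment.
- *That a main trial result is at risk.* Swallowing is a secondary objective (Section 2.2.3), site participation in MBS is optional (Section 4.1.5.7), and analysis is limited to vetted centers (Section 9.5). The 2-year PFS analysis is untouched.

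It is also fair that the harm is partly recoverable, because participating sites upload their MBS videos to a central archive (Sections 4.1.5.7 and 10.1.6, Appendix IX).

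**Conclusion.** The concern holds in a limited form. Appendix VIII is inconsistent between its order rule, its printed list and its rating rule. As listed, items 3 and 4 can be decided by a bolus that the protocol's own reasoning regards as confounded; otherwise, sites may be running different orders. One of six rated boluses is involved, and only patients who do worse on it than on the other five can be scored differently. The effect on prevalence cannot be sized from the documents. The finding assumes that at least some sites read the print order as the order of administration. It is a measurement weakness in a secondary endpoint, worth correcting because the correction is small.

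**What to change.** Reconcile the order sentence, the bolus list and the rating rules in Appendix VIII with one stated rule, applied at every site and visit. Either option would do:

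- Exclude the A-P bolus from the summary rating of penetration and aspiration. No change in procedure; the cost is one fewer rated bolus.
- State that the A-P thin bolus is given before the pudding and cookie. All six boluses stay in the rating; the cost is one extra repositioning of the patient.

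Either is a one-line change. For studies already done, use the archived videos to establish the order actually followed, and run a sensitivity analysis of penetration and aspiration without the A-P bolus. The form records only summary ratings, so this means re-rating from video. The cost is rater time, and it is limited to studies whose uploaded recording shows the bolus order.

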**Lateral view:**

- 5mL thin (2 trials, tsp). Instruction to the patient: *please hold this in your mouth until asked to swallow.*
- 20mL thin (1 trial). Instruction to the patient: *please try to take the whole amount and hold it in your mouth until I ask you to swallow.* Self administration is optimal, but clinician administration is acceptable.
- 5mL pudding (1 trial tsp). Instruction: *swallow when you are ready.*
- 1/2 cookie or cracker, barium coated - coated with 3 ml (1/2 tsp) of Varibar pudding (1 trial). Instruction to the patient: *chew this up and swallow when you feel comfortable and ready to swallow.*

**A-P view:**

10mL thin (1 trial). Instruction: slightly raise your chin (neutral position, not tucked or extended), hold this in your mouth until asked to

**RATING RULES:**

Rate MBS outcomes below on the basis of bolus trials in the ECOG-ACRIN protocol. Do not rate based on additional bolus trials that are administered outside of the protocol or based on bolus trials in which a swallow strategy/posture was tested. Please select a SUMMARY RATING based on the highest level of impairment you observe on any bolus trial in the protocol.

MBS
 Modified Barium Swallow Study Form			
E3311: Phase II Randomized Trial of Transoral Surgical Resection followed by Low-dose or Standard-dose IMRT in Resectable p16+ Locally Advanced Oropharynx Cancer			
1 DATE OF MBS ____ - ____ - ____	2  TIME OF MBS 1. Baseline 2. After surgery (before adjuvant therapy) 3. Six months after treatment 4. Twenty-four months after treatment		
Outcome Variables	Definition	Scoring Rules (Rate the worst of impairment across all bolus trials in the MBS protocol)	Rating
3 LARYNGEAL PENETRATION	PENETRATION: Bolus enters the larynx but does not pass below the TVFs	Select "1" if LARYNGEAL PENETRATION occurred on any bolus in the protocol.	 No penetration (0)  Penetration (1)
4 ASPIRATION	ASPIRATION: Bolus enters the larynx and passes below the TVFs. SENSATE: attempts to eject aspirate from airway (e.g., cough, throat clear) SILENT: no effort to eject aspirate from airway (no cough, throat clear)	Select the highest level of aspiration that occurred during the protocol. Select "1" if SENSATE ASPIRATION occurred on any bolus in the protocol, but silent aspiration NEVER occurred. Select "2" if SILENT ASPIRATION occurred on any bolus in the protocol.	 No aspiration (0)  Yes, sensate (1)  Yes, silent (2)
5 PHARYNGEAL RESIDUE	RESIDUE: bolus remaining on or within the pharynx at the conclusion of the initial swallow. The conclusion of the initial swallow is when the hyoid bone returns to rest. If the patient spontaneously swallows several times to clear the bolus, residue is rated after the 1 st swallow attempt.	Rate the highest level of residue that occurred during the protocol. Select "0" is no residue or only pharyngeal coating occurred during the protocol. Select "1" if pharyngeal residue of <50% of the original bolus remained in the pharynx on any bolus in the protocol. Select "2" if pharyngeal residue of half or more of the original bolus remained in the pharynx on any bolus in the protocol.	 No residue (0)  <50% pharyngeal residue (1)  ≥ 50% pharyngeal residue (2)
PERSON COMPLETING FORM:			

**NOTE:** This form is for reference only. The MBS information for each registered patient will be entered directly into the Medidata Rave database. MBS Videos will be uploaded to a cloud account held by MD Anderson Cancer Center. Instructions on how to upload the videos can be found in Section [4.1.5.7](#).

---

**Phase II Randomized Trial of Transoral Surgical Resection followed by Low-dose or Standard-dose IMRT in Resectable p16+ Locally Advanced Oropharynx Cancer**

**Appendix IX**

**Letter Explaining Modified Barium Swallow Video Upload Instructions**

Dear [CRA SALUTATION],

Thank you for participating in the MBS data collection efforts for ECOG-ACRIN protocol E3311, "Phase II Randomized Trial of Transoral Surgical Resection followed by Low-dose or Standard-dose IMRT in Resectable p16+ Locally Advanced Oropharynx Cancer."

E3311 will archive MBS video files on MD Anderson Cancer Center's Box® Cloud-based storage account. You are receiving this e-mail because you were designated as the individual who will be responsible for uploading and archiving MBS video files to Box.

Details regarding the HIPAA compliance and MD Anderson's Business Association Agreement associated with the Box Cloud account can be found at:

<http://www.mdanderson.org/about-us/for-employees/employee-resources/box-cloud-storage/faqs.html#security>

Additional information regarding the security of Box is located at:

<https://support.box.com/hc/en-us/articles/200526618-Box-HIPAA-and-HITECH-Overview-and-FAQs>

Shortly, you will receive e-mail notification that you have been added as a collaborator to the E3311 MBS Video Files folder on Box. Upon receipt of the e-mail, click on the icon that reads "View Folder." You will then be taken to a webpage that asks you to create an account with Box. When you are ready to upload video files in the future, you will need to return to this site ([www.box.com](http://www.box.com)) and log in. Once logged into your account, click on the shared folder. To upload videos, click on the grey button entitled "Upload" in the top left-hand corner of your screen and select Upload Files from the drop-down menu (please make sure that you are uploading your files inside of this folder). If you forget your password, please click the link labeled "Reset Password" (below the space where you would log into Box) for instructions on obtaining a new password.

To ensure the security of the uploaded video all patient identifiers are to be removed and the video files are to be re-labeled with a unique identification code. To obtain the code:

3. Log the videos into ECOG-ACRIN's *Sample Tracking System* (STS), indicating the "Ship Date" as the date the video is to be uploaded to the MD Anderson Box Cloud Account. Be sure to select the correct protocol-specified time point for the video. (e.g., Baseline, after surgery...)

<https://webapps.ecog.org/Tst/>

4. Exit STS and enter the *Patient Video Identifier Lookup* application. Select the protocol and enter the ECOG-ACRIN E3311 patient identifier to pull up the patient specific information. The code is the "Sample ID" and is a unique code linked to the patient and the time point of the video as entered into STS.

<https://webapps.ecog.org/PatientVideoIdentifyLookup/>

Videos must be uploaded in .mpeg or .avi format. Rename the electronic video file using only the STS-generated sample ID prior to uploading to the MD Anderson Cloud. For example, if the sample ID obtained from STS is "123456" and the video is in .avi format, the file to be uploaded should be named "123456.avi". Any and all PHI contained within the video or as part of its name must be removed prior to upload on Box.

We have attached instructions for saving video files in the desired format as well as editing tips that may be helpful for removing PHI from the MBS videos prior to upload to the Box account.

Should your site have a change in staff responsible for upload of video files to Box, please notify [E3311\\[contact]](mailto:[contact]) with the name and e-mail address of the individual requesting access to Box.

Please do not hesitate to contact us should you need further assistance or encounter problems uploading videos.

Regards,

MD Anderson Cancer Center

Department of Head and Neck Surgery

Section of Speech Pathology and Audiology

T: [contact]

Rev, Add9

**Phase II Randomized Trial of Transoral Surgical Resection followed by Low-dose or  
Standard-dose IMRT in Resectable p16+ Locally Advanced Oropharynx Cancer**

## 1) Objectives

The primary objective is to identify genomic biomarkers in HPV-mediated HNSCC that predict an aggressive tumor phenotype and, thus, patients who should not undergo treatment de-intensification with trans-oral robotic surgery (TORS).

- a. **Objectives:** 1) Develop a predictive model that, using Whole Exome Sequencing and RNA-Seq, predicts risk stratification and clinical outcome after observation, radiation alone, or chemoradiation. Generate a rich genomic and transcriptomic dataset for a novel, rapidly increasing subset of H&N cancers to provide collaborative opportunities for translational research to understand this newly emerging cancer. 2) In an independent set of samples from ECOG 3311, test the one-side null hypothesis that the AUC of the ROC curve of the predictive model is less than 0.6 at  $\alpha=0.05$ . This test is to be performed by the ECOG Statistical Center to ensure independence of the validation from the training.
- b. **Hypotheses:** 1) A predictive model that can be used to predict patients with HPV-mediated who are candidates for de-intensification can be developed using Whole Exome Sequencing and RNA-Seq. 2) In an independent validation set, it can be demonstrated that the AUC of the ROC curve of this predictive model is greater than 0.6.

## 2) Background and Rationale

Traditionally, the major risk factors for Head and Neck Squamous cell carcinoma (HNSCC) were tobacco and alcohol exposure [1-3]. However, HPV is now recognized as the major risk factor for HNSCC of the lingual and palatine tonsils. Molecular and epidemiologic studies have confirmed that nearly 70% of HNSCC of the oropharynx (OPSCC) are HPV-mediated [4, 5]. Risk of death from HPV-mediated OPSCC patients is 50 percent lower than for non-HPV mediated OPSCC. This improvement is portended both by the favorable biology of HPV-mediated OPSCC, but is also related to the younger age and decreased medical comorbidities seen in this patient population. While <15% of HNSCC in the TCGA are HPV-mediated, it has become clear that these tumors have distinct genomic underpinnings compared to non-HPV mediated HNSCC.

[figure not shown]
Favorable tumor biology, in combination with the younger age of HPV-mediated HNSCC patients, leads to not only improved overall survival, but more potential life years after cure. Thus, interest is now focused on reducing treatment-associated morbidity. In particular, attention has been brought to the development of late effects from chemoradiotherapy, as an organ-preservation approach has become a standard of care. In E2399, 49% of OPSCC patients had moderate-to-severe swallowing impairment at 3 months following treatment, and some patients were still PEG dependent after 12 months. Severe swallowing dysfunction following radiation therapy to the oropharynx is a major source of decreased QOL in HPV mediated OPSCC patients.

Traditionally, surgical resection of OPSCC carried significant morbidity due to the difficulty of accessing the oropharynx, necessitating aggressive surgical maneuvers. More recently, trans-oral surgery (TOS) has gained favor as a method for achieving surgical extirpation with limited morbidity. TOS has been shown to be able to achieve complete surgical extirpation of

T1/T2 OPSCC with oncologic outcomes similar to chemoradiotherapy in single institution studies [6]. Further, TOS has improved QOL measures and swallowing outcomes, compared to chemoradiotherapy [6-8]. As expected, patients who receive single-modality TOS have improved swallowing outcomes, compared to patients who receive adjuvant radiation [9]. ECOG 3311 was designed to explore the role of TOS in treatment de-intensification for HPV-mediated OPSCC.

Preliminary evaluation of ECOG 3311 arm stratification has shown that ~30% of patients enrolled were stratified into arm D (tri-modality therapy), based on adverse pathologic risk factors. Tri-modality therapy is well established to have a more severe side effect profile, compared to surgery alone and surgery with adjuvant radiation, particularly, in regards to swallowing. Thus, identification of patients with biologically more aggressive cancers prior to treatment decision-making is vital for avoiding tri-modality therapy, if not absolutely necessary. All patients enrolled in ECOG 3311 have cT1 or T2 and cN1, N2a, or N2b disease, based on clinical or radiographic criteria, and are thus indistinguishable pre-operatively. At this time, no biomarkers exist that predict a more aggressive tumor phenotype or clinical pathologic features that would necessitate stratification into arm D of ECOG 3311 and, thus, tri-modality therapy. ECOG 3311 presents a unique opportunity to investigate such biomarkers in a cohort of HPV+ OPSCC patients with tightly annotated clinical and pathologic data. Of note, [name] is the PI, the highest accruing surgeon nationally to E3311, and personally funded the preliminary genomic/transcriptomic analysis and characterization, using UPMC specimens, to provide feasibility for the proposed studies using additional specimens from this trial.

Our primary preliminary objective was to determine the feasibility of identifying genomic biomarkers that would predict patients who stratify into arm D, pre-operatively. Identifying these patients prior to surgery would allow practitioners to choose alternative therapies, avoiding tri-modality therapy. We first sought to better define the genomic profile of HPV-mediated HNSCC in general. Existing data support HPV-mediated HNSCC having a distinct genomic profile from non-HPV mediated HNSCC [10]. However, a limited number of HPV-mediated HNSCCs had been comprehensively profiled and available to the scientific community. For example, TCGA contains <75 HPV-mediated HNSCCs. From that cohort, and others, we knew that HPV-mediated HNSCC typically lack TP53 mutations, the most common driver mutation in non-HPV mediated HNSCC and CDK2NA alterations, and instead possess high rates of PIK3CA mutations and E2F1 amplifications. However, how specific genomic and transcriptomic alterations relate to tumor behavior within HPV mediated HNSCC is not known. While many potentially promising biologic pathways and hypotheses have been reported to be of importance in HPV mediated HNSCC, for example, the presence of TRAF3/CYLD mutations has been shown to correlate with tumor behaviors [11], to date, no established biomarkers exist.

[figure not shown]
To determine if the approach was feasible, we generated and analyzed WES and RNA-Seq datasets for 40 patients from the University of Pittsburgh. Briefly, after pathologic review, DNA and RNA was extracted from 43 HNSCC tumors (FFPE), as well as germline DNA from peripheral blood. One patient had low quality nucleic acid on QC and was removed. Tumor and germline DNA underwent WES at 85% of targeted bases at 50X or greater coverage (~150X MTC) paired end reads for the tumor DNA and 85% of targeted bases at 20X or greater coverage (~60X MTC) for germline DNA. Tumor RNA underwent RNA-Seq at 50M paired end reads at the Broad Institute using standard library prep and sequencing approaches (76-bp paired end on Illumina HiSeq 2500). Two patients had low coverage or failed fingerprint SNP analysis and were removed. Our workflow for the remaining 40 patients is represented in **Figure 1**. More detailed methods are presented in Laboratory Methods.

